**Step 1: Propensity Score to Treatment** We plan to structure the study analysis of observational data in SA1 to mimic a randomized clinical trial: a) assignment of coronary intervention (INT) vs. medical therapy (MED) is based on the therapy selected in the initial 60 days after imaging and b) nonrandomized treatment adjusted for via a propensity score. Either PCI or CABG will define coronary revascularization. Follow-up time begins at the time of the index stress CMR imaging. To adjust for non-randomization of treatment, a single propensity score will be developed using logistic regression to model the decision to refer to revascularization considering all factors known to influence the referral decision. This single composite propensity score represents the probability of treatment assignment, which will be included in all subsequent survival models (step 2) associating stress CMR perfusion guided-treatment with the respective endpoints in each of the 3 sub-aims. This adjustment reduces the bias introduced by nonrandomized referral to INT in practice. While all factors known to influence this referral decision will be considered for entry into this logistic regression model, based on existing literature, the most likely predictors of referral to INT include % ischemic myocardium (% myocardial mass based on number of segments, by CMR), typical angina symptoms (yes if positive response to 2 of 3 Diamond and Forrester qualities, else no), infarct size (LGE size, grams of myocardial mass), ischemic ST changes on rest ECG (yes/no), pre-test coronary disease probability (ordinal), and prior cardiac catheterization (yes/no). We anticipate that 10-15% of patients (~n=300) received INT so model over-fitting will not occur when constructing this logistic regression model.

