## Appendix Section

### A1: Diamond and Forrester Chest Pain Prediction Score to restrict enrollment to intermediate (moderate) to high risk pre-test likelihood of disease.

#### III. Interpretation

##### A. Typical Angina: 3 criteria from above

1. Age 30-39: 76% likelihood (intermediate) in men and 26% in women (intermediate)
2. Age 40-49: 87% likelihood (high) in men and 55% in women (intermediate)
3. Age 50-59: 93% likelihood (high) in men and 73% in women (intermediate)
4. Age 60-69: 94% likelihood (high) in men and 86% in women (high)

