##### B. Atypical Angina: 2 criteria from above

1. Age 30-39: 34% likelihood (intermediate) in men and 12% in women (low)
2. Age 40-49: 51% likelihood (intermediate) in men and 22% in women (low)
3. Age 50-59: 65% likelihood (intermediate) in men and 31% in women (intermediate)
4. Age 60-69: 72% likelihood (intermediate) in men and 51% in women (intermediate)

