##### C. Non-Anginal Chest Pain: 1 criteria from above

1. Age 30-39: 4% likelihood (low) in men and 2% in women (low)
2. Age 40-49: 13% likelihood (intermediate) in men and 3% in women (low)
3. Age 50-59: 20% likelihood (intermediate) in men and 7% in women (low)
4. Age 60-69: 27% likelihood (intermediate) in men and 14% in women (intermediate)

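### The propensity score's yes/no typical angina variable conflicts with the symptom classes in Appendix A1 and discards symptom information; the resulting bias is probably small.

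*Combined protocol and SAP*

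**What the plan says.** Statistical Analyses, Specific aim 2, Step 1 (Propensity Score to Treatment) plans one logistic model for referral to early revascularization (INT) rather than medical therapy (MED). It states that "the most likely predictors of referral to INT include % ischemic myocardium" and five further items. One of the five is "typical angina symptoms (yes if positive response to 2 of 3 Diamond and Forrester qualities, else no"; another is "pre-test coronary disease probability (ordinal". The score is one "which will be included in all subsequent survival models (step 2" of the Aim 2 analysis.

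Appendix A1 sets out the Diamond and Forrester classes by number of criteria met: "Typical Angina: 3 criteria from above", "Atypical Angina: 2 criteria from above" and "Non-Anginal Chest Pain: 1 criteria from above", with a separate low-risk entry for patients who meet none. For each class it gives a likelihood of disease by age band and sex, for example "Age 50-59: 93% likelihood (high) in men and 73% in women (intermediate" for typical angina.

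Data to Collect, a) Patient Demographics, says that Diamond and Forrester symptom scores will be recorded. No section says that the propensity variable is meant to pool typical and atypical angina.

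**The concern.** One named variable has two definitions that cannot both be right. Symptom class plausibly drives both the decision to revascularize and the outcome, which is why Step 1 lists it. If the score blurs a distinction that clinicians acted on, part of the confounding by symptoms stays in the INT versus MED comparison. The Step 2 Cox models do not recover it directly, because the other risk markers named there are age, sex, diabetes and percent ischemic myocardium.

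There is also a problem of reproducibility. Step 1 does not say whether two means at least two or exactly two, so two programmers could build different scores from the same text. If the pre-test probability is taken from A1, a patient with two criteria could be typical in one covariate and atypical in another within the same model.

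**Working it through.** The plan states no figure that rests on this definition, so there is none to reproduce. The check sets the two definitions side by side, measures how far apart the pooled classes are in A1, and then asks what the pooling could do to the hazard ratio.

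**1. The definitions**

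| Criteria met | Appendix A1 | Step 1, read as at least 2 | Step 1, read as exactly 2 |
|---|---|---|---|
| 3 | typical | yes | no |
| 2 | atypical | yes | yes |
| 1 | non-anginal | no | no |
| 0 | none | no | no |

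Neither reading reproduces A1's typical class.

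**2. Distance between the pooled classes.** Difference = A1 likelihood for typical minus A1 likelihood for atypical, in percentage points, with the A1 risk class in each case.

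| Age | Men | Risk class, men | Women | Risk class, women |
|---|---|---|---|---|
| 30-39 | 76 - 34 = 42 | intermediate, intermediate | 26 - 12 = 14 | intermediate, low |
| 40-49 | 87 - 51 = 36 | high, intermediate | 55 - 22 = 33 | intermediate, low |
| 50-59 | 93 - 65 = 28 | high, intermediate | 73 - 31 = 42 | intermediate, intermediate |
| 60-69 | 94 - 72 = 22 | high, intermediate | 86 - 51 = 35 | high, intermediate |

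The range is 14 to 42 points. The risk class differs in 6 of 8 strata; the exceptions are men aged 30-39 and women aged 50-59. These are gaps in disease likelihood. They show that the classes differ, not how much confounding follows.

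**3. Make-up of the yes group under at least 2.** The documents give no symptom mix. Assuming atypical-to-typical ratios of 1:3, 1:1 and 3:1, the atypical share of the yes group is 1/4 = 25%, 1/2 = 50% and 3/4 = 75%.

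**4. Possible effect on the hazard ratio.** This needs the symptom mix and the links from symptoms to referral and to outcome, none of which the documents give. The simulations are therefore illustrative. Their assumptions are a true INT hazard ratio of 1, referral odds multiplied by 2 to 3 and hazard by 1.3 to 1.6 per symptom step, a 40/35/25% mix of 1, 2 and 3 criteria, and cohorts of 2,200. Age, sex and ischemia distributions were also assumed. Shifts are measured against three-level coding.

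| Coding in the score | Shift in INT hazard ratio |
|---|---|
| At least 2, no pre-test probability | about +0.03 to +0.12 |
| At least 2, with A1 ordinal risk class | about +0.01 to +0.035 |
| Binary cut at 3 | about +0.03 to +0.06 |

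Two cautions apply. First, the shift is not the same as bias. In one set of runs three-level coding itself gave 0.954 to 0.993 and at-least-2 coding gave 0.995 to 1.104, so against the true value of 1 the latter was off by -0.005 to +0.104. Second, the standard deviation of the log hazard ratio across cohorts was 0.14 to 0.18. A shift of 0.035 near a hazard ratio of 1 is about 0.034 on the log scale, and 0.034/0.14 is about a quarter of one standard deviation.

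**The case against.** The best case for leaving the plan alone has four parts.

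- **The same sentence supplies an offset.** Ordinal pre-test probability is also listed, and in A1 it depends on symptom class, so it restores much of the distinction between two and three criteria. This largely stands and is the main reason to expect a small effect. It is not assured: listed factors are only considered for entry, and the plan does not say that the pre-test probability comes from A1. Specific aim 1 lists pre-test probability and the Diamond and Forrester score as separate markers.
- **A cut at two or more can be a legitimate covariate.** A propensity score needs predictors of referral, not diagnostic labels, and the predictor list cites published work that may have used this coding. That is fair, but such a variable is typical-or-atypical angina and should be named and justified as such.
- **A1 is headed as an enrollment tool.** True, and the list of the three criteria is not visible. The counts that define each class are visible, and A1 is the only place where the document defines the classes.
- **The model is not fixed.** Finer coding remains open, and the plan compares key risk markers between treatment groups without and with matching. Neither the openness nor the comparison settles which definition will be programmed.

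A reader might go further and infer that the Aim 2 treatment estimate is materially biased, or that the cost-effectiveness result is affected too. The documents support neither. They give no symptom mix and no association with referral. Aim 3 is linked only through the propensity matching named in its statement of aim; the decision analysis described under Statistical Analyses has no stated propensity step.

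**Conclusion.** The contradiction is certain: Step 1 and Appendix A1 define typical angina differently under either reading of Step 1, and nothing reconciles them. As written, the rule discards symptom information in a score that enters the Aim 2 survival models. The patients are misclassified only relative to A1.

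The size of any bias cannot be derived from the documents. Under the simulation assumptions above, the shift in the INT hazard ratio is about 0.01 to 0.035 if an A1-based ordinal pre-test probability stays in the score, and up to about 0.1 if it does not. The first range is well inside sampling error. The upper figure should not be read as the expected bias, because it leaves out a covariate that the plan lists and is measured against a comparator that does not itself sit exactly at 1.

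The point is worth correcting because the inconsistency is plain and the correction nearly free, not because the Aim 2 result is shown to be wrong.

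**What to change.** In Step 1, replace the yes/no variable with the Appendix A1 symptom class (none, 1, 2 or 3 criteria), entered as a categorical term and built from the Diamond and Forrester scores already collected. State also whether the ordinal pre-test probability is derived from A1, since that decides how much the two covariates overlap.

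Keep the level for none if numbers allow: the enrollment criteria admit patients on an abnormal ECG, so some may meet no symptom criterion.

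Do not simply move the binary cut to three. That would match the A1 label but merge atypical with non-anginal patients, and in the simulations it still left a shift of about 0.03 to 0.06.

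The cost is one sentence and no new data. The yes/no variable uses one degree of freedom. The four-level term uses three, which is two more; merging none with one criterion uses two, which is one more. Step 1 expects 10-15% of 2,200 to receive INT, that is 0.10 × 2,200 = 220 to 0.15 × 2,200 = 330 patients, so the model can carry this.

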### **Specific aim 3**

A decision analysis will be performed and it compares stress CMR perfusion imaging based on all cost and outcome data obtained in this study, against the current cost-effectiveness data from SPECT imaging and coronary CTA. It has been shown recently that coronary CTA-only strategy demonstrated a favorable incremental cost effectiveness ratio (ICER) of \$20,429 per QALY, which is

both cheaper and more effective than SPECT imaging (dominated) for evaluation of intermediate-risk chest pain patients without known coronary artery disease.

Using CMR data collected from the current proposal study, we anticipate that a base-case model (a 55 year-old male with 30% CAD prevalence) of comparative cost-effectiveness analysis can be constructed using published diagnostic performance of CAD diagnosis from other modalities: coronary CTA (95% sensitivity, 83% specificity, equivocal rate 0.12), SPECT (87% sensitivity, 73% specificity, equivocal rate 0.09), and invasive coronary angiography (100% sensitivity, 100% specificity).

We plan to perform a decision analysis and compare the following strategies (a) coronary CT angiography followed by invasive coronary angiography for positive or equivocal findings for CAD at coronary CT angiography (coronary CT angiography only), (b) coronary CT angiography followed by invasive coronary angiography for positive findings for CAD at coronary CT angiography and myocardial perfusion SPECT for equivocal findings for CAD at coronary CT angiography (coronary CT angiography first), (c) myocardial perfusion SPECT followed by invasive coronary angiography for positive or equivocal findings for CAD at myocardial perfusion SPECT (myocardial perfusion SPECT only), (d) stress CMR perfusion followed by invasive coronary angiography for positive or equivocal findings for CAD at CMR perfusion (myocardial perfusion CMR only), and (e) direct invasive coronary angiography. Using costs and QALY data we collect from the current proposed study, a base-case model (55 year-old male with 30% CAD prevalence) of cost-effectiveness analysis can be constructed using published diagnostic performance of CAD diagnosis: coronary CTA (95% sensitivity, 83% specificity, equivocal rate 0.12), SPECT (87% sensitivity, 73% specificity, equivocal rate 0.09), and invasive coronary angiography (100% sensitivity, 100% specificity). From published meta-analyses, stress CMR perfusion had reported a 89-92% sensitivity, and 80-90% specificity.

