### **Specific Aim 3 – Cost-effectiveness analysis**

Using a propensity score-matching analysis, test the hypothesis that in real-world clinical practice that stress CMR perfusion imaging-guided use of INT offers *cost-effectiveness benefits* over MED in patients with suspected ischemia.

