### **Specific aim 2 (2 separate analyses for sub-aims 2.1 and 2.2, respectively)**

We structured the present study's analysis of observational data to mimic a randomized clinical trial: a patient's assignment to a treatment was based on the therapy selected in the first 60 days after stress CMR perfusion study and nonrandomized treatment adjusted for via a propensity score. This time point of 60 days was selected from previous work indicating that revascularization performed within this timeframe resulted from the noninvasive imaging study, whereas referrals after 60 days tended to be attributable to worsening clinical status. Based on our pilot data, approximately 10-15% of patients undergo early coronary revascularization within the first 60 days after CMR. We therefore anticipate that 85-90% of the study cohort received MED whereas 10-15% received INT.

We plan to examine the assumptions of proportional hazards in each of the Cox models. In addition, performance of the propensity score model will be tested by comparing the prognostic associations between treatment and clinical outcomes, without and with that propensity score matching. Key risk markers will be compared between the treatment groups, without and with inclusion of the propensity score matching.

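### Aim 3 is stated as a propensity-matched cost-effectiveness test of INT versus MED, but the only analysis detailed for it ranks five diagnostic strategies and cannot answer that hypothesis

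*Combined protocol and SAP*

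**What the plan says.** The aim statement (Specific Aim 3 – Cost-effectiveness analysis) is one sentence. It opens "Using a propensity score-matching analysis, test the hypothesis that in real-world clinical practice" and ends with the claim that CMR-guided INT "offers *cost-effectiveness benefits* over MED in patients with suspected ischemia". It therefore fixes a contrast (INT versus MED), an outcome (cost-effectiveness) and a method (propensity matching).

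The analysis text (Statistical Analyses, Specific aim 3) begins "A decision analysis will be performed and it compares stress CMR perfusion imaging based on all cost and outcome data obtained in this study", with SPECT and coronary CTA as comparators. It continues "We plan to perform a decision analysis and compare the following strategies" and lists (a) to (e): CTA only, CTA first, SPECT only, CMR only, and direct invasive angiography. The population is hypothetical: "a base-case model (55 year-old male with 30% CAD prevalence) of cost-effectiveness analysis can be constructed" from published diagnostic accuracy together with the study's cost and QALY data.

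The propensity score is described only under Specific aim 2, whose heading reads "2 separate analyses for sub-aims 2.1 and 2.2, respectively". Step 1 says the score will be "included in all subsequent survival models (step 2) associating stress CMR perfusion guided-treatment with the respective endpoints in each of the 3 sub-aims". Step 2 is a set of Cox models and names sub-aims 2.1 and 2.2 only. The expected treatment split is that "85-90% of the study cohort received MED whereas 10-15% received INT".

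Inputs for an economic comparison are listed under Data to Collect: unit costs in d) Costs and 4-year QALYs in e) Effectiveness. QALY is also a secondary outcome under Study Endpoints.

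**The concern.** The hypothesis and the detailed analysis ask different questions. The hypothesis compares two treatments among patients who have all had stress CMR. The decision model compares tests, and most of them were not the cohort's index strategy.

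Two things could go wrong. A ranking of imaging strategies could be reported under a hypothesis about revascularization. Or an INT-versus-MED cost result could be produced with its estimand, estimator and interval chosen once the data are known, since the available text fixes none of them. The Rationale section offers the three aims as core evidence for insurers' payment decisions, and whether revascularization is worth its cost is a different payer question from which test is.

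**Working it through.** The plan gives no sample size, power or precision figure for Aim 3 (Sample Size covers sub-aim 1 and sub-aim 2.3 only), so there is no stated figure to reproduce. The check is a comparison of texts.

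**1. Aim statement against analysis text**

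| Element | Aim statement | Statistical Analyses, Specific aim 3 |
|---|---|---|
| Contrast | INT versus MED | Five diagnostic strategies |
| Population | Real-world patients with suspected ischemia | One hypothetical profile: male, 55, 30% CAD prevalence |
| Method | Propensity score matching | Decision analysis |
| Use of propensity score | Named | Not mentioned |
| INT or MED arm or branch | Both arms | None described |

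The CMR strategy, (d), is described only as far as invasive angiography after a positive or equivocal scan. What follows angiography is not specified for any strategy.

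**2. Can the model's output answer the hypothesis?** The hypothesis needs the difference in mean cost and in mean QALY between INT and MED, adjusted for non-random referral. The model as described yields expected cost and QALY for each testing strategy. A difference between two testing strategies is not a difference between two treatments, so no ranking of (a) to (e) bears on the hypothesis.

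**3. Is the comparison specified elsewhere?**
- Specific aim 2, Step 1 defines the treatment groups, the 60-day window and the score, then places the score in survival models.
- Step 2 fits Cox models for sub-aims 2.1 and 2.2. These give hazard ratios, not incremental costs or QALYs.
- Data to Collect d) and e) define inputs, not an estimator.
- Study Endpoints lists QALY without an analysis.

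No available section gives an estimator of the INT-minus-MED difference in cost or QALY, a willingness-to-pay threshold or an uncertainty method.

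**4. Size of the groups if the comparison is kept.** From Specific aim 2: 0.10 × 2,200 = 220 and 0.15 × 2,200 = 330 INT patients, which fits the figure of about 300 in Step 1. The remainder is 1,870 to 1,980 MED patients.

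**5. Are the listed costs enough for that comparison?** Under d) Costs, medical care covers acute MI, heart failure and unstable angina admissions, and heart transplantation. Imaging tests and cardiac procedures are also listed. Medication, outpatient and stroke costs are not, although stroke is a secondary outcome. Under a) Patient Demographics, medications are recorded as at the time of imaging. On the listed inputs, the continuing drug cost of either treatment cannot be computed.

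**The case against.** The strongest defence is that the plan is under-specified, not silent. The aim statement belongs to the plan and names a method, and the treatment groups, score, costs and QALYs are all defined somewhere. That stands: a reader might infer that Aim 3 has no INT-versus-MED method at all, and the documents do not support that. The accurate statement is that the decision model is the only Aim 3 analysis *detailed*.

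A second defence is that a model with costs and QALYs must represent what happens after angiography, so INT and MED could be downstream branches. That is possible, but none is described, and nothing says that such branches would take propensity-adjusted inputs.

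A third concerns the three sub-aims mentioned in Step 1. A reader might take these to be 2.1, 2.2 and 2.3, and so conclude that the score was never meant for Aim 3. The documents do not settle this. Sub-aim 2.3 is a comparison with a historical rate and names no propensity score, whereas the three hypotheses that do name propensity matching are 2.1, 2.2 and Aim 3. The score may well have been intended for Aim 3. On either reading the sentence concerns survival models and supplies no cost or QALY estimator.

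A reader might also infer that matching would leave too few pairs, for example by confining it to patients with ischemia. The plan sets no such restriction and no matching ratio, and Steps 1 and 2 enter the score as a model term, where a pair count does not apply. With no cost or QALY standard deviation in the documents, neither adequate nor inadequate precision can be shown.

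Finally, d) Costs refers to an attached figure and a budget file that were not available. They are cited for costs, not for a treatment comparison, but the statements here are limited to the text at hand.

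**Conclusion.** The mismatch holds. As detailed, the Aim 3 analysis addresses a different question from its stated hypothesis and could not support or reject it. This affects one of the three specific aims and leaves Aims 1 and 2 untouched. It should be corrected before any cost-effectiveness result is reported.

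The conclusion rests on the wording of the aim statement and of the analysis section, and on two conditions: that the decision model has no treatment branches beyond those described, and that the unavailable cost attachments contain no INT-versus-MED analysis. It depends on no numerical assumption. The 220-330 INT patients bear only on how informative an added comparison could be. They do not show that it would be underpowered.

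**What to change.** Make the hypothesis and the analysis agree, by one of two routes.

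**(a) Restate the aim.** Reword Specific Aim 3 as the model-based comparison of imaging strategies already detailed, and make no cost-effectiveness claim for INT versus MED. This costs wording only.

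**(b) Keep the hypothesis and add its analysis.** Under Statistical Analyses, Specific aim 3, specify an INT-versus-MED comparison of 4-year costs and QALYs, using the treatment groups, 60-day window and score from Specific aim 2. State:
- whether the score is used for matching or for adjustment, since the aim says matching and Steps 1 and 2 describe a model term;
- how incomplete 4-year follow-up is handled;
- the quantities reported: incremental cost, incremental QALY, and the ICER or net benefit at a stated willingness-to-pay threshold;
- a bootstrap interval for these.

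Label the decision model as a separate analysis.

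Route (b) needs no new patients, but it is more than a wording change. The INT group is small, about 220-330. The listed cost inputs omit medication, outpatient and stroke costs, and medications are recorded only at imaging. Either further cost inputs are added, or the result is labelled as limited to the listed cost components.
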